8.4.2 Method of Detecting AEs and SAEs

Care will be taken not to introduce bias when detecting AEs and/or SAEs. Open-ended and non-leading verbal questioning of the participant is the preferred method to inquire about AE occurrences.

Version 5.0 Page: 46 of 68

8.4.3 Follow-up of AEs and SAEs

After the initial AE/SAE report, the investigator is required to proactively follow each participant at subsequent visits/contacts. All SAEs will be followed until resolution, stabilization, the event is otherwise explained, or the participant is lost to follow-up (as defined in Section 7.3). Further information on follow-up procedures is provided in Section 10.3.

8.4.4 Regulatory Reporting Requirements for SAEs

Prompt notification by the investigator to the sponsor of an SAE is essential so that legal obligations and ethical responsibilities towards the safety of participants and the safety of a study intervention under clinical investigation are met.

The sponsor has a legal responsibility to notify both the local regulatory authority and other regulatory agencies about the safety of a study intervention under clinical investigation. The sponsor will comply with country-specific regulatory requirements relating to safety reporting to the regulatory authority, Institutional Review Boards (IRB)/Independent Ethics Committees (IEC), and investigators.

An investigator who receives an investigator safety report describing an SAE or other specific safety information (e.g., summary or listing of SAEs) from the sponsor will review and then file it along with the Investigator's Brochure and will notify the IRB/IEC, if appropriate according to local requirements.

For all studies except those using medical devices, investigator safety reports must be prepared for suspected unexpected serious adverse reactions (SUSAR) according to local regulatory requirements and sponsor policy and forwarded to investigators as necessary.

8.4.5 Pregnancy

A subject's participation is to be terminated immediately if a pregnancy is supposed (i.e. in case her pregnancy test becomes positive). The investigator must report to the sponsor any pregnancy occurring in a female subject during her participation in this study. The outcome of the pregnancy should be followed up carefully, and any outcome of the mother and the child at delivery should be reported.

If a pregnancy is reported while participant is in the Treatment phase, the investigator will record pregnancy information on the appropriate form and submit it to the sponsor within 24 hours of learning of the female participant's pregnancy.

While pregnancy itself is not considered to be an AE or SAE, any pregnancy complication or elective termination of a pregnancy for medical reasons will be reported as an AE or SAE.

Abnormal pregnancy outcomes (e.g., spontaneous abortion, fetal death, stillbirth, congenital anomalies, ectopic pregnancy) are considered SAEs, and will be reported as such.

Any post-study pregnancy-related SAE considered reasonably related to the study intervention by the investigator will be reported to the sponsor as described in Section 8.4.4. While the investigator is not obligated to actively seek this information in former study participants, he or she may learn of an SAE through spontaneous reporting.

For all reports, the forms provided are to be used. The investigator should submit them within the same timelines as an SAE (see Section 10.3.4). Send the completed pregnancy forms to:

[contact]

Version 5.0 Page: 47 of 68

8.5 Pharmacokinetics

PK and pharmacodynamic parameters are not evaluated in this study.

8.6 Genetics or Pharmacogenomics

Genetics are not evaluated in this study.

8.7 Biomarkers

Biomarkers are not evaluated in this study.

8.8 Immunogenicity Assessments

Not Applicable

8.9 Health Economics

Health Economics parameters are not evaluated in this study.

Version 5.0 Page: 48 of 68

9. Statistical Considerations

Statistical analysis will be performed using statistical analysis software (SAS) and the version used will be specified in the Statistical Analysis Plan (SAP) and placed on file. The SAP will contain a more comprehensive explanation than described below of the methodology used in the statistical analyses. The SAP will also contain the rules and data handling conventions used to perform the analyses, and the procedure used for accounting for missing data.

9.1 Statistical Hypotheses

The primary efficacy endpoint is the duration of episode (DOE). The treatment comparison between Sitavig and placebo will be made as 2-sided at the significance level of 0.05. No multiplicity adjustment will be made.

9.2 Sample Size Determination

9.3 Analysis Set

For the purposes of analysis, the following analysis sets are defined:

Table 2 - Analysis Populations

| Participant Analysis Set | Description |
|--------------------------|--|
| Safety | All randomized subjects who take at least one dose of IMP. Safety analyses will be conducted on the safety population. |
| Intent To Treat (ITT) | All subjects who are randomized and provide at least one measure of primary efficacy parameters after the 1 st dose of IMP. |
| Per Protocol (PP) | The Per Protocol population will include all subjects in ITT who complete 14-days of evaluations and do not have any major protocol violations. Any exclusion from PP Population will be determined and documented prior to the database lock. |
| | The primary efficacy analysis population will be PP population and ITT Population will be secondary. The same analysis on ITT Population will be repeated for the primary and secondary efficacy endpoints to assess the robustness of the results based on PP Population. |

Version 5.0 Page: 49 of 68

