8.1.5 Treatment/Evaluation Phase (Days 1 through 14)

8.1.5.1 Day 1-2 (Visit 2)

Within 36 hours after the start of study intervention, participants will present for Visit 2. Visit 2 can be performed on Day 1 or Day 2. The following procedures will be done for this visit:

- Review inclusion/exclusion criteria
- Review concomitant medications;
- Sitting BP and pulse after at least 5 minutes in a sitting position;
- Review Science 37 Platform data for completeness;
- Review study intervention kit (drug accountability);
- Review used/unused pregnancy test kits for signs of use;
- Adverse Event assessment.

Participants will record face images and complete 0-10 NRS HL symptom evaluation at 09:00, 14:00 and 19:00 that day in the Science 37 Platform. All post-dose time point assessments have an allowable window of ± 60 minutes.

8.1.5.2 Day 3

The following procedures will be done by the participant:

- Face images at 09:00, 14:00 and 19:00 that day;
- 0-10 NRS cold sore symptom evaluation at 09:00, 14:00 and 19:00 that day;
- QoL-OHIP at 09:00 that day;

All post-dose time point assessments have an allowable window of ± 60 minutes.

8.1.5.3 Days 4, 5 and 6

The following procedures will be done by the participant for each day:

- Face images at 09:00, 14:00 and 19:00 each day;
- 0-10 NRS cold sore symptom evaluation at 09:00, 14:00 and 19:00 each day.

All post-dose time point assessments have an allowable window of ± 60 minutes.

8.1.5.4 Day 7

The following procedures will be done by the participant:

- Face images at 09:00, 14:00 and 19:00 that day;
- 0-10 NRS cold sore symptom evaluation at 09:00, 14:00 and 19:00 that day;
- QoL-OHIP at 09:00 that day.

All post-dose time point assessments have an allowable window of ± 60 minutes.

Page: 40 of 68

Version 5.0 Page: 41 of 68

8.1.5.5 Days 8, 9, 10, 11, 12 and 13

The following procedures will be done by the participant:

- Face images at 09:00, 14:00 and 19:00 each day;
- 0-10 NRS cold sore symptom evaluation at 09:00, 14:00 and 19:00 each day;

All post-dose time point assessments have an allowable window of ± 60 minutes.

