4 DEFINITIONS AND DERIVATIONS

Run-in Failures: Run-in failures are participants who successfully completed screening and randomized to a blinded study intervention (treatment). Participants start a 6-month eligibility window during the Run-in Phase where they could potentially self-initiate treatment. Participants who are considered a Run-in failure occur because of the following:

- Randomized participants with no prodromal symptoms after 6 months
- Met an exclusion criterion (e.g., medication, pregnancy)
- Adverse event or change in medical history that requires study withdrawal
- Withdraw of informed consent by the participant
- Study intervention kit not available
- Lack of compliance as determined by the Investigator/designee

Baseline: Baseline value is defined as the last non missing assessment prior to first administration of the study drug. If the assessment occurs on the same day as the first study drug administration, then the time of assessment should be compared to the time of first dose administration to derive the baseline value.

Post-baseline: The Post-baseline values are defined as assessments taken after the first administration of study drug/treatment.

Change from Baseline = $(post\ baseline\ value - baseline\ value)$.

Duration of Episode (DOE): DOE is defined as the time from the initiation of treatment to the healing of primary lesions (loss of crust) for subjects who experience a vesicular lesion. For subjects whose primary lesions are not vesicular in nature, DOE is the time from study intervention initiation to the return to normal skin as determined by the independent blinded reader of the subject's face images using a 6-point Likert scale or the cessation of symptoms, whichever comes last. For the subjects who do not demonstrate the healing of primary lesions or cessation of symptoms, the data will be censored at 14 days (14*24 hours) regardless of any circumstances. If time (hour) is missing for either treatment initiation or the healing of primary lesion or both, however, both dates are recorded, then DOE is number of days (end date – start date) *24. If only healing ending date and/or time are missing, DOE will be imputed as 14*24 hours. If date of treatment initiation is missing, then DOE will be missing.

CONFIDENTIAL Page 17 of 31

Private and Confidential Study No 21755 Date: DEC 18, 2023

DOE (hours) = (Date and time of healing of primary lesions – Date and time of first treatment administered)

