Vesicular lesion: A lesion will be categorised as vesicular if a subject has face image interpretation Likert scale score of 3 or above.

Healing of primary lesions: A vesicular lesion will be considered as healed if the face image interpretation Likert score drops to either 0 or 1 after progressing to 3 and beyond. For those without a vesicular lesion, healing is defined as a face image interpretation Likert score of 0 or cessation of symptoms i.e., all NRS symptom scores as 0, whichever comes last.

Cessation of symptoms: Cessation of symptoms is defined as the absence of sensations of pain, tenderness tingling, itching or discomfort at the site of the cold sore as measured by NRS. In other words, having the NRS score of 0 for all symptoms such as pain, tingling, tenderness, itching and discomfort is cessation of symptoms.

Time to cessation of symptoms: It is the time (in hours) from the initiation of treatment dose of assigned study intervention to cessation of symptoms. For the subjects who do not demonstrate the cessation of symptoms, the data will be censored at 14 days (14*24 hours) regardless of any circumstances. If hour is missing for either treatment initiation or the endpoint but both dates are recorded, then Time to cessation of symptoms is number of days (end date – start date) multiplied by 24. If either date is missing, then Time to cessation of symptoms is missing.

 $\it Time\ to\ cess at ion\ of\ symptoms = (Date\ and\ time\ of\ cess at ion\ of\ symptoms - Date\ and\ time\ of\ first$

treatment administered)

Time to recurrence of HL lesions: It is the time (in days) from resolution of the cold sore treated in the Treatment phase until appearance of a cold sore during the follow-up period. The time to first recurrence is determined by assessment from the investigator and documented using NRS symptom scores and face images using the Science 37 Platform. For subjects who do not recur during the follow-up period, the data will be censored at the time of last follow-up.

Time to recurrence of HL lesions (Days) = (Date of first recurrence of HL lesions – Date of healing of primary lesions) + 1

CONFIDENTIAL Page 18 of 31

Private and Confidential Study No 21755 Date: DEC 18, 2023

Treatment Emergent Adverse Event: A TEAE is defined as any new AE that commences on or after the start of the first study drug administration or any pre-existed AE/ condition that worsened in severity following administration of study drug.

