6 ANALYSIS POPULATION AND TREATMENT GROUPS

6.1 Analysis Population

Screened Population: All subjects who signed the Informed Consent Form.

Safety Population: All randomized subjects who take at least one dose of IMP.

Intent-to-treat (ITT) Population: All subjects who are randomized and provide at least one measure of primary efficacy parameters after the first dose of IMP i.e., if there is at least one non-missing assessment of subject's face image using a 6-point Likert scale after study drug initiation.

PP Population: The Per Protocol population will include all subjects in ITT who complete 14-days of evaluations and do not have any major protocol violations. Any exclusion from PP Population will be determined and documented prior to the database lock.

Follow-Up Population: The Follow Up population will be a subgroup of the ITT population who will continue into the 12 month follow up period and will be defined as patients whose lesions were all treated at the end of the Treatment Phase (of 14 Days) of the trial.

CONFIDENTIAL Page 20 of 31

Private and Confidential Study No 21755 Date: DEC 18, 2023

The primary efficacy analysis population will be PP population and ITT Population will be secondary. The same analysis on ITT Population will be repeated for the primary and secondary efficacy endpoints to assess the robustness of the results based on PP Population.

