7.7 Efficacy Analysis

7.7.1 Analysis of Primary Efficacy Endpoint

The primary efficacy variable is DOE, which will be measured in hours (using the Science 37 Platform), of a single treated HL lesion. Observation period to determine healing will last up to 14 days. DOE is defined in detail in section 4.

DOE will be analyzed using Kaplan-Meier method for treatment groups (Sitavig and Placebo). Median, associated 95% CIs and survival probabilities will be estimated using Kaplan-Meier (KM) Method. DOE curves between the two treatment groups will be compared with a log-rank test and the corresponding hazard ratio (with 95% CI) will be estimated using Cox proportional hazard method.

The analysis of primary efficacy endpoint will be performed on both ITT and PP population, with PP population being the primary efficacy population and ITT population being secondary. Individual subject data for DOE will be presented in Listing.

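### The primary test of episode duration uses a Per Protocol set whose undefined 14-day completion rule can drop participants whose healing has already been observed

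*Protocol*

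**What the plan says.** Protocol 9.3 (Table 2) sets the order of populations: "The primary efficacy analysis population will be PP population and ITT Population will be secondary". SAP 7.7.1 repeats it for DOE, "with PP population being the primary efficacy population and ITT population being secondary".

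The PP definition is the same in both documents. SAP 6.1: "The Per Protocol population will include all subjects in ITT who complete 14-days of evaluations and do not have any major protocol violations". Neither document says what completing means, how many missed assessments are tolerated, or what happens once a lesion has healed. Protocol 9.3 adds a safeguard: "Any exclusion from PP Population will be determined and documented prior to the database lock".

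The ITT set needs only one scored "face image using a 6-point Likert scale after study drug initiation" (SAP 6.1). It is therefore a modified ITT: participants who never dosed or have no post-dose image fall outside it.

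SAP section 4 fixes the event: "A vesicular lesion will be considered as healed if the face image interpretation Likert score drops to either 0 or 1", after having reached 3 or more. A lesion that never becomes vesicular needs a score of 0 and all symptom scores at 0. The image schedule runs to Day 14 with no stop at healing (Protocol 8.1.5.3 and 8.1.5.5: "Face images at 09:00, 14:00 and 19:00 each day").

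For participants not seen to heal, Protocol 9.4.2 censors at 14 days or at loss to follow-up, whichever is earlier. SAP section 4 differs: "the data will be censored at 14 days (14*24 hours) regardless of any circumstances". SAP 7.13, which lists changes from the protocol, does not mention this.

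**The concern.** The trial randomizes against placebo, hypothesizes that the tablet shortens the episode, and tests the difference two-sided at 0.05 (Protocol 1.1 and 9.1). The primary population should therefore keep the randomized groups as intact as the data allow.

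Once a vesicular lesion has been scored as healed, the SAP definition gives its DOE. Later images are not needed to compute it. Under a literal PP rule, a participant who stops photographing a healed lip is nevertheless removed from the primary log-rank test. Faster healers have longer left in which to stop, so membership is tied to the outcome. At stake are upward-shifted medians, lost power and, if the arms stop at different rates, a biased primary comparison. Because completion is undefined, the size of the primary set is also settled by a reading chosen after healing data exist.

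**Working it through.** The plan has no readable figure to reproduce: Protocol 9.2 shows no text and SAP 2.3 is redacted. The steps below use the schedule and stated assumptions.

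**1. Images left after healing is scored** (three per day to Day 14).
- 144 h after dosing falls on Day 7. Days 8–14 give 7 × 3 = 21, plus 0 to 2 later on Day 7: **21 to 23**.
- 240 h falls on Day 11. Days 12–14 give 3 × 3 = 9, plus 0 to 2: **9 to 11**.

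**2. How much the reading of completion matters.**
- Visit 3 attendance: nobody is excluded if all attend.
- Every image on Days 2–14 (13 × 3 = 39), each obtained independently with probability 0.95, 0.98 or 0.99: 0.95^39 = 13.5%, 0.98^39 = 45.5% and 0.99^39 = 67.6% of participants qualify.
- A Day 14 entry: see steps 3 to 6.

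**3. Chance that a healed participant fails the Day 14 reading**, 1 − exp(−h × days left), where h is the assumed daily stopping rate.

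| Healed at | Days left | h = 2% | h = 5% |
|---|---|---|---|
| 96 h | 10 | 1 − exp(−0.20) = 18% | 1 − exp(−0.50) = 39% |
| 240 h | 4 | 1 − exp(−0.08) = 8% | 1 − exp(−0.20) = 18% |

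**4. Equal stopping in both arms, no loss before healing.** Assumptions: Weibull healing times with shape 2, medians 144.0 h and 144.0 + 0.57 × 24 = 157.7 h, 500 per arm, log-rank test. The 0.57 days is the earlier trial's gain in healing time of the primary lesion (Protocol 2.2), not DOE. The implied hazard ratio is (157.7/144.0)² = 1.20.

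| Stopping per day | Excluded from PP | Medians (h) | Power |
|---|---|---|---|
| none (ITT) | 0% | 144 / 158 | 81% |
| 1% | 7% | 147 / 161 | 79% |
| 2% | 13.5% | 150 / 164 | 77% |
| 5% | 30% | 158 / 175 | 73% |

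**5. Adding loss before healing** (exponential at 1%, 2%, 4% per day), same model, 500 per arm. Power:

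| Lost before healing | ITT, Protocol 9.4.2 censoring | PP | ITT, SAP censoring at 336 h |
|---|---|---|---|
| 6% | 77–79% | 70–74% | 60–63% |
| 12% | 74–76% | 63–70% | 48–49% |
| 23% | 70–72% | 56–60% | 36–38% |

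Separate runs of this model agree within about three points and keep the same order. Major protocol violators were not modelled.

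**6. No drug effect, 200 per arm, null medians of 144 and 157.7 h.** Equal stopping rejects in 4.8–5.7% of runs and ITT in 4.9–5.0%. Stopping at 2% versus 3% per day rejects in about 6%, and 2% versus 4% in about 8–10%. A different model gives a wider range: log-normal times, 250 per arm, and only those healed before Day 7 stopping. There, 30% versus 20% stopping rejects in 6.9% of runs and 40% versus 20% in 18%.

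**The case against.** **Later images can matter.** Participants dose in the prodrome, before visible signs, when the lip can still score 0. A non-vesicular lesion with score 0 and no symptoms meets the healing definition, yet may become vesicular later, and no rule requires healing to be sustained. A reader might infer that DOE is always known at the first healing score. The SAP definitions do not support that. For lesions not yet vesicular, a 14-day requirement has a real rationale, so the concern is weaker there. For a vesicular lesion that has fallen back to 0 or 1, it stands.

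**Safeguards exist.** The trial is double-blind, exclusions are fixed before database lock, and the same analysis is repeated on ITT. These limit arm-driven choices. They do not stop selection on healing time, and ITT remains a secondary check.

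**Participants who keep to the schedule stay in.** Healing early excludes nobody by itself, and under the Visit 3 reading a participant who skips images but attends also stays. This stands: the effect could be close to nil.

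**ITT is not automatically better.** With SAP censoring at 336 h, ITT has less power than PP in step 5. This stands too, and it is why the population and the censoring rule must change together. ITT also admits protocol violators.

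**Conclusion.** The point holds in a limited form and should be fixed. Both documents make PP primary, leave completion undefined, and give no exemption after a vesicular lesion has healed. Read literally, observed event times can be discarded from the primary test for reasons related to healing time.

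A reader might infer that this inflates type I error or favours the active arm. The documents do not support either. In the model, equal stopping leaves type I error near 5%, and the hazard ratio at 1.20 to 1.22 against 1.20 for ITT. Bias needs stopping that differs by arm, its direction depends on which arm stops more, and nothing in the documents shows such a difference.

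The sizes are illustrative. They rest on an assumed Weibull shape, assumed medians, assumed stopping and loss rates, arm sizes of 200 and 500, and the Day 14 reading. Confidence is medium, because the sample size, the stopping rate and the meaning of completion are all unavailable.

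**What to change.** 1. In Protocol 9.3 and SAP 6.1, 7.7.1 and 7.7.2, make the existing ITT population primary for DOE and aborted lesions, with PP supportive. Describe it as modified ITT.
2. Together with (1), replace the SAP section 4 censoring of DOE at 336 h with the Protocol 9.4.2 rule: the earlier of loss to follow-up or 336 h. SAP 3.3 already limits the 14 × 24-hour imputation to participants whose lesions are healed. Make the looser imputation sentence in section 4 carry the same limit.
3. In the supportive PP set, do not exclude a participant solely for evaluations missed after a vesicular lesion has been scored as healed. Keep the Day 14 requirement for lesions that have not become vesicular, and state what satisfies it.

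SAP section 4 does not settle how a participant lost before healing counts for aborted lesions. Any rule chosen should be labelled as new.

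The cost is wording plus one DOE derivation. Both populations are already planned and no new data are needed. The downside is that the primary set will contain protocol violators, which may dilute the effect slightly.

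Separately, Protocol 6.4 leaves participants unblinded during the Treatment Phase out of that phase's analysis, while the ITT and Safety definitions carry no such exclusion. Those passages must be reconciled as a point of their own.
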